1.5 Background

In 2009, approximately 719,000 females in the United States were newly diagnosed with various types of cancer.¹ Nearly 17% of these new cancer cases were diagnosed in reproductive age females.¹ The most common cancers diagnosed in females of childbearing age are breast and cervical carcinoma, melanoma, non-Hodgkin's lymphoma, leukemia and colon cancer.²⁻⁴ Of these, breast is the most common malignancy site for females and is the second leading cause of cancer-related deaths in females.

Approximately 4 in 100 adults today is a cancer survivor.⁵ With the recent advancements in cancer detection and treatment, survival rates are increasing for cancer patients. Over the past 30 years, the number of cancer survivors in the United States has increased to almost 14 million.⁵ As a result; there is a tremendous focus on improvement of quality of life in cancer survivors. When a female is diagnosed with cancer, particularly a young female, issues regarding survival are paramount; however, the magnitude of reproductive health and quality of life issues cannot be neglected.⁶

The definition of reproductive health is widely accepted as “the state of complete physical, mental and social well-being, and not merely the absence of reproductive disease or infirmity.”⁷ The components that define reproductive health are broad and not well defined in the literature. For the purpose of this proposal, we define the components of reproductive health as it pertains to females with cancer as oncofertility, oncocontraception, and sexuality. The initial period of cancer diagnosis and treatment is fraught with much uncertainty regarding reproductive health issues related to prognosis of disease, iatrogenic loss of fertility, endocrine disruption, and exposure to teratogenic treatment agents.

Fertility preservation for young cancer survivors has obtained research and public interest; however, reproductive health is not only limited to fertility preservation but also includes sexuality and family planning, ranging from oncocontraception, preconception counseling, and optimization of present or future pregnancy.⁸ The full scope of reproductive health is often omitted from the discussion of cancer treatment planning.

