1.6 Summary and Rationale for Proposed Study

Uncertainties regarding future fertility, pregnancy and cancer survival are intricate and challenging for a patient and a cancer care team. The goals of comprehensive reproductive health care at times may come in conflict with the primary objective of cancer care. However, with appropriate counseling and preventive measures, this conflict can be absolved to unify objectives. Work from

this study should inform leading organizations in cancer care and treatment to improve guidelines and to include a reproductive health assessment for all young females with cancer. It would also aid informed decision making and management plans.

This interventional study involves an initial assessment of reproductive health for females with cancer. Various modalities will provide data on the prevalence of reproductive health care needs during the course of cancer care. Based on this reproductive health assessment, a management plan pertaining to reproductive and sexual health is developed in conjunction with the cancer management plan. Measurable outcomes pertaining to management and treatment implementation and modification are the cornerstones of this study. Study tools have been tested by our research group at four institutions and are feasible for administration.

As this is a behavior study, details pertaining to the intervention are included in addendum I and are only accessible to those sites randomized to receive the intervention. It is requested that the details of the intervention remain confidential to maintain the integrity of the randomized cluster-controlled design. If local IRBs have questions or concerns regarding the intervention, they are instructed to contact ECOG-ACRIN or the study team directly.

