Additionally alterations in thyroid function have been noted in females with breast cancer with a baseline rate of autoimmune thyroid disease 2-3 times the general population.¹⁴ Thyroid function may be affected by chemotherapy and radiation treatment, particularly when treatment is localized to the vicinity of the thyroid.¹⁵ Such disruption may lead to symptoms that may affect quality of life indicators related to sexuality and sexual health. Repercussions of these effects remain an important aspect of research within oncology care. Given the available data, many questions remain unanswered; therefore, the laboratory ancillary included in this proposal would provide important data during the course of our primary study.

This data will provide a foundation for future research to aid prediction of fertility status throughout the course of cancer care and treatment.

This analysis will be performed at Quest Diagnostics.

Rev. Add9

1.8 Quality of Life (QOL) Assessment: Longitudinal Study of Sexuality in Females with Newly Diagnosed Cancer

Rev. Add11

We propose a prospective observational study performing interval sexuality surveys for reproductive aged females throughout 2 years post diagnosis of cancer.

Hypothesis

Primary Hypothesis: Cancer survivors' sexual function decreases during initial cancer treatment then increases with time after treatment completion.

Secondary Hypothesis: Cancer survivors have lower levels of satisfaction with their sex lives compared to the age-matched general population at baseline.

Background

Sexuality remains an important aspect of reproductive health that is greatly influenced by cancer diagnosis and treatment. The extent of impact of cancer diagnosis and treatment is poorly understood. Sexuality encompasses gender roles, patterns of affection, social and family roles, and genital sex, and affects a survivor physically, psychologically, and emotionally.¹⁶ It should be understood that sexuality is "an ever-changing, lived experience affecting the way in which people view themselves, their body and their ability to intimately connect with significant others throughout life, rather than limiting it to fertility status or capacity for sexual intercourse."¹⁷

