5.10 Quality of Life (QOL) Assessment

The Sexual Function Survey will be administered to all patients recruited for the EROS study over the 2 year study period (as specified in Table 1). The PROMIS Sexual Function Brief Profile v1.0 - Female measures are included in the Sexual Function Survey.

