8.6.4 Plan for Longitudinal Study of Sexuality

Measurement of PROMIS Sexual Function Survey Brief Profile v1.0 - Female will be used to evaluate the hypotheses that (1) cancer survivors' sexual function decreases during primary cancer treatment then increases after treatment completion and (2) cancer survivors have lower levels of satisfaction with their sex lives compared to the age-matched general population at baseline. All patients recruited for the EROS study will be included in this part of analysis. Data collected in PROMIS Sexual Function Survey Brief Profile v1.0 - Female in the EROS study will be summarized and plotted across time with respect to each of the subdomains (global satisfaction with sex life, interest in sexual activity, lubrication, vaginal discomfort, and orgasm). A linear mixed-effect model will be used to study changes in each of the subdomain scores of PROMIS Sexual Function Survey Brief Profile v1.0 - Female over time, with institution as the random effect (by stratum and across all patients if there is no difference between strata). For the secondary hypothesis, our comparative group is the

Rev. Add9

Rev. Add8

age-matched population of non-cancer females in the reproductive age range surveyed by the Duke Clinical Research Institute. The collaborator at Duke Clinical Research Institute will provide summary data on age-matched non-cancer patients. The PROMIS study uses a *T* score method with a mean of 50 and a standard deviation of 10. Results from the Sexual Function Survey in the EROS trial will be transformed into *T* scores as well then comparison between the groups will be performed using the two-sample *t* test.

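### The sexual-function model in section 8.6.4 pools both randomised arms with no stated arm or arm-by-time term, so about 35% of any change confined to Arm B would enter the time trend

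*Combined protocol and SAP*

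**What the plan says.** Section 5.10 sets the collection: "The Sexual Function Survey will be administered to all patients recruited for the EROS study over the 2 year study period". Both arms therefore contribute. Section 8.6.4 sets the analysis population, "All patients recruited for the EROS study will be included in this part of analysis", and then the method: "A linear mixed-effect model will be used to study changes in each of the subdomain scores" of the PROMIS profile over time, "with institution as the random effect (by stratum and across all patients if there is no difference between strata"). The hypothesis to be read from that trend is in section 1.8: "Cancer survivors' sexual function decreases during initial cancer treatment then increases with time after treatment completion". The only comparison between groups in 8.6.4 is of trial patients with an external age-matched population without cancer; the hypothesis behind it concerns baseline.

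Two earlier sections bear on whether arm matters for this outcome. Section 1.5 says "we define the components of reproductive health as it pertains to females with cancer as oncofertility, oncocontraception, and sexuality". Section 1.6 says that, after the reproductive health assessment, "a management plan pertaining to reproductive and sexual health is developed in conjunction with the cancer management plan".

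Elsewhere the plan does use arm. Section 8.6.1 compares the arms on appropriate management, contraception and pregnancy, and section 8.6.2 summarises patient and clinician ratings by arm.

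**The concern.** By the protocol's own description, the programme delivered at Arm B sites may act on sexual health. Arm B is then not simply more usual-care follow-up for this outcome. A time trend fitted to both arms together mixes the course under usual care with the course under the programme, and a model without arm cannot separate them.

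Two things are at stake. The first is how the section 1.8 hypothesis is read. If the programme improves function after treatment, the pooled curve rises more than usual care alone would. If it protects function during treatment, the pooled curve falls less. The second is a randomised comparison on sexual function that the trial could make with data it already collects, but which the supplied text does not plan.

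**Working it through.** **Where arm could have entered.** Section 8.6.4 names change over time, an institution random effect and a split by stratum. Section 8.6.2 covers ratings, reproductive choices and predictors of adequate management. Section 8.10 adds joint modelling of dropout for longitudinal data without mentioning arm. No supplied section compares sexual function by arm.

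**Weight of Arm B in the pooled trend.** Section 8.4 projects 276 Arm A and 149 Arm B patients, 425 in total.

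- Weight = 149/425 = 0.351.
- Shift in the pooled trend = 0.351 × (change confined to Arm B). For assumed changes of 2, 3 and 5 T-score points, the shift is 0.70, 1.05 and 1.75 points, with no change at all in Arm A. With equal arms the weight would be 0.5.

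The institution random effect does not remove this. In a simulated mixed model with an institution random intercept, the pooled time change was 1.08 for a 3-point Arm B effect, 1.79 for 5 points and -0.03 for none. With arm and arm-by-time added, a true 5-point Arm B effect came back as an interaction of 4.72, with an Arm A change of 0.14 (true value 0). Some fits gave convergence warnings, but the pooled results agree with the analytic weight.

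**Precision of the usual-care trajectory.** If it is read from Arm A, the SE ratio to the pooled estimate is about √(425/276) = 1.24, taking information as proportional to the number of patients.

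**Power of the unplanned arm contrast.** The plan gives no sample size or power for sexual function. As a check on method, I reproduced the plan's primary-endpoint figure: 50% against 80%, 8 clusters per arm, mean size 15, CV 0.8, ICC 0.10, two-sided alpha 0.10.

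- Design effect = 1 + ((1 + 0.8²) × 15 - 1) × 0.10 = 3.36.
- SE = √(3.36 × (0.25 + 0.16)/120) = 0.107.
- Power (noncentral t, 14 df) = 0.845, against 0.85 stated.

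For sexual function at one follow-up visit the inputs are:

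- From the documents: SD 10 (PROMIS scale, 8.6.4); 9 and 8 enrolling sites and CV 0.78 (8.3); two-sided alpha 0.10 and 5% ineligible, borrowed from the primary endpoint.
- Assumed: within-patient correlation 0.5, attrition 20-30%, ICC 0.01 to 0.10. The protocol adopts 0.10 for the primary endpoint and gives no ICC for this one.

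The formulas are:

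- Residual SD after baseline adjustment = 10 × √(1 - 0.5²) = 8.66.
- Design effect in each arm = 1 + ((1 + 0.78²) × m - 1) × ICC.
- SE = 8.66 × √(DE_A/n_A + DE_B/n_B), with 15 df.

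At 20% attrition, n_A = 276 × 0.95 × 0.80 = 209.8 (m = 23.3) and n_B = 149 × 0.95 × 0.80 = 113.2 (m = 14.2). At ICC 0.10 the design effects are 4.65 and 3.18, and the SE is 1.94 points.

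| ICC | Power, 3 points | Power, 5 points |
|---|---|---|
| 0.01 | 0.77-0.81 | 0.99 |
| 0.05 | 0.56-0.58 | 0.91-0.92 |
| 0.10 | 0.42-0.43 | 0.78-0.79 |

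Each range runs from 30% to 20% attrition. No allowance is made for five subdomains. Stratum 3 is not sexually active, so lubrication, discomfort and orgasm may have fewer respondents than these numbers.

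**The case against.** The strongest reply is that this component was never meant to test the programme. Section 1.8 introduces it thus: "We propose a prospective observational study performing interval sexuality surveys for reproductive aged females throughout 2 years post diagnosis of cancer". Objective 2.4.1 asks only for a longitudinal study, and the hypotheses concern the time course and a comparison with the general population. That stands to this extent: the plan does not contradict its own objective, and the arm contrast is an addition. But the observational label does not turn Arm B into a usual-care cohort, and the time-course question is itself affected.

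The model description is also brief, so arm is unmentioned rather than excluded. In addition, section 8.1 places endpoint details in Addendum II, which was not supplied. A reader might infer that the randomised comparison is never made. The documents support only that it is not planned in the text available.

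A reader might also infer that any programme effect would be mistaken for recovery. That is too strong. Only about 35% of an Arm B change enters the trend, and an effect during treatment would work the other way, by hiding the decline. Nor can a false-claim rate for recovery be drawn from the documents. It would need no recovery at all under usual care, contrary to the plan's hypothesis, and an Arm B gain for which the protocol gives no basis. The baseline comparison with the general population is unaffected if baseline scores precede the intervention.

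Finally, testing the hypothesis on Arm A patients alone would discard about 35% of a cohort declared to include everyone. That is a fair objection to restricting the data, but not to adding model terms.

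**Conclusion.** The point holds in a limited form. As written in the supplied documents, 8.6.4 describes a trend pooled over two arms that may differ on this outcome, and states nothing that would separate them. The weight of 0.351 follows directly from the projected accrual. How far the trend would actually move depends on the programme's effect on sexual function, which is unknown; the 2-, 3- and 5-point cases are illustrations.

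The arm contrast is informative but not strongly powered across the plausible range. It is good for 5 points at low ICC, just under 0.80 at ICC 0.10, and weak for 3 points unless the ICC is near 0.01. It should be read as an estimate with its interval. The primary endpoint analysis and the contraception analyses are not affected.

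**What to change.** In section 8.6.4, for each subdomain:

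- Add arm and arm-by-time to the mixed model, keeping all patients and institution as the cluster. Code time as visit and, for the section 1.8 hypothesis, as during versus after treatment. Months from baseline alone do not identify treatment phase.
- Present the trajectories by arm, and read the usual-care course from the Arm A estimates in that joint model.
- Report the baseline-adjusted arm contrast as a secondary or exploratory estimate with a confidence interval, stating how five subdomains will be handled and how many patients answer each.
- If Addendum II already includes arm, align 8.6.4 with it.

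The cost is analysis-plan wording and a few model terms, with no new data collection. The price in precision is an SE for the usual-care trajectory about 1.24 times that of the pooled one.

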5.7.2 Patient Reported Outcomes Assessment Schedule

If a patient is eligible to participate in this study and the physician approves, the study is further discussed with the patient. Patients providing consent will be registered on trial. Participants will complete a total of 8 assessment visits (including baseline). Structured interviews will be administered to participants at the timepoints listed below. At each time point, two questionnaires will be administered by a study team member. Completion of these forms on a given visit should take about 10-20 minutes. Patient interviews are designed to assess the patient's reproductive health history, management and goals at baseline and as they progress through cancer treatment. Additionally, the Sexual Function Survey, which includes the PROMIS Sexual Function Brief Profile v1.0 – Female, is designed to assess sexual health at diagnosis and throughout treatment.

Patients will be assessed according to the following schedule:

Rev. Add8

Patient Baseline Interview (51 Questions)

Baseline

Patient Follow-Up Interview (34 Questions)

1. 3 Months from Baseline Visit
2. 6 Months from Baseline Visit
3. 12 Months from Baseline Visit
4. 24 Months from Baseline Visit

Patient Interview - During Chemotherapy/Radiation Treatment (11 Questions)

In addition to the above forms, each patient will complete the **Patient Interview During Chemo/Radiation Treatment** as well according to the following schedule:

Within one week prior to the start of each chemotherapy regimen for patients undergoing chemotherapy or every four weeks of RT for patients undergoing radiation therapy alone

Sexual Function Survey (16 Questions)

1. Baseline
2. Within one week prior to the start of each chemotherapy regimen for patients undergoing chemotherapy or every four weeks of RT for patients undergoing radiation therapy alone
3. 3 Months from Baseline Visit
4. 6 Months from Baseline Visit
5. 12 Months from Baseline Visit
6. 24 Months from Baseline Visit

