	0.5	11	0.96	0.90	0.83
	0.6	12	0.96	0.90	0.82
	0.7	14	0.97	0.90	0.82
	0.8	17	0.97	0.90	0.81
10	0.0	8	0.96	0.91	0.87
	0.5	9	0.96	0.90	0.84

Number of Clusters (k, per arm)	Coefficient of Variation (CV)	Mean Cluster Size (m)	ICC		
			0.05	0.10	0.15
	0.6	10	0.96	0.90	0.84
	0.7	11	0.97	0.90	0.83
	0.8	12	0.97	0.90	0.81

Based on the results in the Verma and Lê's study²⁶, it is estimated that the intra-cluster correlation coefficient for the primary endpoint is 0.10. As of January 4, 2021, 9 Arm A sites and 8 Arm B sites have had enrolled patients for the EROS trial (n=268 for Arm A and 138 for Arm B) with CV=0.78 (=23.9/18.6). Assuming ICC=0.10, 16 institutions in total (i.e., 8 clusters per arm) and CV=0.8, Table 1 indicates an average of 27 eligible patients per cluster can detect an improvement from 50% to 80% while keeping 0.10 two-sided type I error rate and 90% power. Due to the slow accrual in Arm B, the study power was lowered to 85% with an average of 15 eligible patients per cluster, keeping the other parameters constant. In this case, this study requires 240 eligible patients in total enrolled into this study (average of 15 per cluster, 120 per arm) in order to keep 0.10 type I error rate and 85% chance of detecting the proposed 50% to 80% improvement on the primary endpoint. Assuming a 5% ineligibility rate and an additional 15% of attrition rate at 3 months (based on the fourth interim analysis with data pulled in July 2019), the sample size for the primary endpoint of this study is inflated to 298 patients in total (149 patients per arm, across the four strata), under equal enrollment on the two arms. To obtain 149 intervention arm cases, total enrollment will need to be 425 patients (see below).

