8.10 Handling Missing Data

The primary analysis will treat missing data as missing at random then analyze cases with complete data. The method of multiple imputation will be used to handle missing data if more than 20% of the cases have missing data in the variables of interest. If so, sensitivity analysis will be performed to compare results from the complete case analysis and imputation analysis. In case of discrepancies, possible explanations will be discussed. For longitudinal data, given the expected high level of missingness in these data, data will be analyzed according to the methods described in Schluchter and in Schluchter, Greene, and Beck^{28,29}. These methods take into account the possibility of informative missingness by jointly modeling the longitudinal response and the time to dropout.

9. Correlative Studies

NOTE: Effective March 10, 2021 the endocrine marker sub-study is closed to further accrual. This sub study has met its targeted accrual goal.

Serum specimens should continue to be collected from previously enrolled patients that have consented to provide serum specimens at the time points outlined below.

Do not submit serum specimens from patients registered to E1Q11 after March 10, 2021.

NOTE: THIS SECTION APPLIES TO BOTH STUDY ARMS.

Rev. 5/17

NOTE: ECOG-ACRIN requires that all biological samples submitted be entered and tracked via the online ECOG-ACRIN Sample Tracking System. An STS shipping manifest form must be generated and shipped with the sample submissions. See Section [9.4](#).

NOTE: An informed consent must be signed prior to the submission of any samples for laboratory studies. Samples for the optional laboratory studies should be submitted only from patients who have given written consent for the use of their samples for these purposes.

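### Section 8.6.4 names institution as the random effect for repeated sexual-function scores, with no patient-level term and no link to 8.10; fitted as written, inference on change over time is wrong

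*Combined protocol and SAP*

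**What the plan says.** Section 1.8 gives the sub-study's primary hypothesis: "sexual function decreases during initial cancer treatment then increases with time after treatment completion". Section 5.7.2 schedules the "Sexual Function Survey (16 Questions" at baseline, at 3, 6, 12 and 24 months, and at treatment visits. Section 5.10 adds: "The Sexual Function Survey will be administered to all patients recruited for the EROS study over the 2 year study period".

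Section 8.6.4 states "All patients recruited for the EROS study will be included in this part of analysis" and specifies a linear mixed-effect model for change in each subdomain score "over time, with institution as the random effect (by stratum and across all patients if there is no difference between strata". It names no other random effect and no within-patient covariance. It gives no test or alpha for deciding whether strata differ.

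Section 8.10 says: "For longitudinal data, given the expected high level of missingness in these data, data will be analyzed according to the methods described in" two cited papers. It describes those methods as allowing for informative missingness by "jointly modeling the longitudinal response and the time to dropout". Neither section cites the other. Section 8.10 gives no random-effect structure and does not say whether its model replaces, extends or checks the one in 8.6.4.

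**The concern.** The hypothesis concerns change within patients. In repeated scores on the same women, the within-patient correlation is usually the main dependence. A model whose only random effect is institution puts the patient variance into the residual and treats two surveys from one woman as no more alike than surveys from two women at the same site.

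This has three consequences:

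- The standard error of visit-to-visit change ignores the covariance that makes change more precise.
- The likelihood cannot use a woman's earlier score to allow for her later dropout, although 8.10 expects much missing data.
- Comparisons of mean level between strata count repeated surveys as independent patients.

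At stake are the power and validity of the analysis serving the quality-of-life objective (2.4) and the decision to pool strata.

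**Working it through.** The plan gives no standard error, power or sample size for this analysis, so there is no figure to reproduce.

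**Inputs from the plan.** Projected accrual is 425 patients at 17 sites (8.4). Six-month attrition is about 20% (8.5.1, 8.5.2), so 425 × 0.80 = 340 surveys at 6 months. Three-month attrition comes from "an additional 15% of attrition rate at 3 months" (8.3). The CV of cluster size is 0.78 (8.3). The T-score SD is 10 (8.6.4); this is the scaling constant of the instrument, not an observed trial SD.

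**Assumptions.** Within-patient correlation ρ = 0.3 / 0.5 / 0.7 after the institution effect, and compound symmetry. Every accrued patient is taken to give a baseline survey.

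**1. Standard error of mean change, dropout unrelated to score, no site-by-visit variance**

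- As written: 10√(1/n₀ + 1/n₁) = 10√(1/425 + 1/340) = 0.728.
- True SE of the same estimate: 10√(1/n₀ + 1/n₁ − 2ρ/n₀).
- Ratio, with q = n₁/n₀: √[(1 + 1/q)/(1 + 1/q − 2ρ)]. The SD and the absolute numbers cancel.

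| Baseline to 6 months | ρ = 0.3 | ρ = 0.5 | ρ = 0.7 |
|---|---|---|---|
| SE as written | 0.728 | 0.728 | 0.728 |
| True SE | 0.623 | 0.542 | 0.447 |
| Ratio | 1.17 | 1.34 | 1.63 |
| SE with a patient term, same data | 0.619 | 0.529 | 0.414 |
| Change detectable with 80% power as written, two-sided 5% | 1.95 | 1.88 | 1.80 |
| The same with a patient term | 1.73 | 1.48 | 1.16 |

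Detectable change as written is 1.96 × 0.728 + 0.84 × true SE; with a patient term it is (1.96 + 0.84) × the patient-term SE. Section 8.6.4 states no alpha, so 5% is a choice. For baseline to 3 months (q = 0.85) the ratios are 1.17 / 1.36 / 1.67. With complete pairs they are 1/√(1 − ρ) = 1.20 / 1.41 / 1.83.

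**2. Dropout that depends on the baseline score**

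Assume a true change of zero, 80% retained at 6 months, and a logit slope for retention of 1 per SD of the baseline score. The mean standardised baseline score among those retained is then 0.173. Their expected 6-month mean is shifted by 10 × ρ × 0.173 = 0.5 / 0.9 / 1.2 points. The institution-only analysis compares that mean with the full baseline mean, so the shift becomes bias. Simulated rejection of the true null at nominal 5% is about 7 / 14 / 32%; a 20,000-run simulation without an institution effect gave 8 / 16 / 34%. At a slope of 0.5 per SD, rejection is about 4 to 5%.

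**3. When the SE error reverses**

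*Mean change varies by site.* Let each site-by-visit effect have variance τ². It adds 2τ²(1 + CV²)/17 = 2τ²(1 + 0.78²)/17 = 0.189τ² to the variance of mean change. The excess being offset is 2ρ × 100/425 = 0.141 / 0.235 / 0.329. They balance at τ² = 0.75 / 1.24 / 1.74, that is, about 1 to 2% of a total variance of 100. Above that, the SE as written is too small.

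*A single slope is fitted.* For complete visits at 0, 0.25, 0.5, 1 and 2 years, Sxx = 2.5. Per patient, the slope variance as written is (100 + 2.5σ²/5)/2.5, and the true one is σ² + 100(1 − ρ)/2.5, where σ is the SD of patient slopes. They are equal when σ² = 50ρ, so σ = 3.9 / 5.0 / 5.9 points per year. Above that, the SE as written is too small.

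**4. Differences in mean level between strata**

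Over five complete visits, the variance of a patient's mean is 100(1 + 4ρ)/5, against 100/5 as written. The SE is too small by √(1 + 4ρ) = 1.48 / 1.73 / 1.95-fold. This is illustrative, since the plan defines no such test.

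**The case against.** The strongest defence is that 8.10 already directs longitudinal data to a joint model. Dropout time belongs to the patient, so such a model needs a patient-level link; on this reading 8.6.4 names institution only to reflect clustering, and what is missing is a cross-reference. That is a fair reading of intent. It does not settle the matter, because 8.10 states no structure and 8.6.4, read alone, is a complete model with one random effect. Addendum II, cited in 8.1 for endpoint details, was not available and may supply the term.

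The inputs are also open to challenge. The correlations and the dropout mechanism are assumed, and the SD is a scaling constant. The 425 includes patients who may prove ineligible. The contrasts use calendar visits, whereas the hypothesis concerns treatment and its completion. This limits the figures in points, but the ratios in step 1 depend only on ρ and q.

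A reader might infer that the error is merely conservative and cannot produce a false finding of change. The documents do not support this: 8.10 expects substantial and possibly informative missingness, and steps 2 and 3 show over-rejection and reversal under modest assumptions. Nor do they support the opposite inference, that ignoring repeated measures must make the SE of change too small; step 1 shows the reverse when dropout is unrelated to score and change is uniform across sites.

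**Conclusion.** The point stands: 8.6.4 states no patient-level term for scores repeated on the same patients, and 8.10 is not reconciled with it. Fitted as written, the inference on change over time is wrong, but its direction is not fixed. With dropout unrelated to score and no variation in change by site, the SE of the 6-month change is 1.17 / 1.34 / 1.63 times too large, at a cost in power. With score-dependent dropout, a true null may be rejected well above 5%. Site-by-visit variance or widely varying patient slopes can reverse the SE error. All sizes rest on the assumptions shown.

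A reader might extend this to the trial's main result. The documents give no ground for that: 8.6.1 analyses the primary endpoint by GEE with institution as the cluster, and the arm comparison does not use the 8.6.4 model. The effect is confined to the observational sexuality sub-study. The change should be made before analysis but is not critical to the trial.

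**What to change.** In 8.6.4:

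- Specify a patient random intercept nested within institution, or an unstructured within-patient covariance plus an institution effect.
- Use the same structure for the comparison that decides pooling across strata, and state how that decision will be made.
- Fit a site-by-visit term as a sensitivity analysis. A patient term alone does not cover variation in change between sites. Because it shortens the SE, it leaves a larger shortfall if such variation exists.
- State whether the 8.10 joint model is the main or a sensitivity analysis for these scores, and that it carries the same patient-level structure. The patient term deals with dropout that depends on observed scores; dropout that depends on unobserved scores is the case for the joint model.

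If Addendum II already states a patient-level term, align 8.6.4 with it. The cost is SAP wording and slightly more analysis work; no new data are needed.
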